## Version history

This Statistical Analysis Plan (SAP) amendment 2 for study 207495 is based on the protocol amendment 4 (Version: GSK Document Number TMF-14577505), Dated 20-Apr -2022.

SAP Version	Approval Date	Protocol Version (Date) on which SAP is Based	Change	Rationale
SAP	11-DEC-2019	2017N336101_00 (30-SEP-2019)	Not Applicable	Original version
SAP amendment 1		TMF-14577505 (20-Apr-2022)	
 
1) Migrated the SAP to new SAP template released on March 2021. Sections/Section number were updated accordingly. Added Section 6 supporting documentation to the SAP.
 
2) Section 1.2 updated to incorporate changes made in protocol amendment 2 and protocol amendment 3 including End of Study definition
 
3) Section 2.1 updated to incorporate changes to the information fraction for the interim PFS analysis (and now based on first 120 participants randomized) and introduction of an additional interim OS analysis made in protocol amendment 2
 
4) Section 4.7 updated to incorporate changes to the event trigger for the interim PFS analysis and an additional interim OS analysis made in protocol amendment 2
 
5) Section 4.7.1 align text with changes made in protocol amendment 2
 
6) Section 5.2 updated to incorporate changes to the event trigger for the final OS analysis, estimated timing for the final OS analysis and removal of enrolment cap for North East Asia Countries made in protocol amendment 2 and protocol amendment 3
 
7) Section 4.2, 4.3.1, 4.3.2: Remove piecewise constant Hazard ratio analysis according to protocol amendment 2. Non-proportional hazards will be handled by Restricted Mean Survival Time (RMST) method; specified analyses based on mITT population.
 
	Updated based on protocol Amendment 2, protocol Amendment 3 and protocol Amendment 4 Further clarification

SAP Version	Approval Date	Protocol Version (Date) on which SAP is Based	Change	Rationale
			
8) Section 4.2.1: move the planned analyses to Section 4.2.2
 
9) Section 4.2.2: remove the sensitivity analysis of supplementary estimand 1 and 2 on investigator response
 
10) Section 4.2.2: Minor updates to the footnote of PFS censoring rule for more clarification;
 
11) Section 4.3.1.3 Added sensitivity analysis for OS censoring any subjects who started a subsequent anti-cancer treatment
 
12) Section 4.3.2: Clarify the timing of analyses for secondary efficacy endpoints per updates in the protocol amendment 2; update analysis methods for TTP.
 
13) Section 4.3.2.1: Add response confirmation algorithm.
 
14) Section 4.3.2.1 Removed supplementary analyses of supportive secondary efficacy endpoints based on the mITT
 
CCI
 
16) Section 4.3.2.4 remove summary of change of fatigue domain in QLQ-C30 and IL52 by responder status
 
CCI
 
18) Section 4.5.2: Add safety analyses for COVID-19.
 
19) Section 4.5.3.1: Update analyses for ocular exam findings based on protocol amendment 1.
 
20) Section 4.5.3.2: Add KVA analyses based on protocol amendment 2.
 
21) Section 4.3.2.4: Update Secondary PRO analyses based on protocol amendment 2. Added more clarifications to the analyses.
 
CCI
	

SAP Version	Approval Date	Protocol Version (Date) on which SAP is Based	Change	Rationale
			
CCI [REDACTED] expression levels in the main SAP.
 
23) Section 4.5.4.3: Remove summary analyses for ECG since protocol amendment 2 removed routine ECG monitoring;
 
CCI [REDACTED]
 
CCI [REDACTED]
 
CCI [REDACTED]
 
27) Section 4.5.1: Update dose intensity and duration of exposure analyses for belantamab mafodotin arm
 
28) Section 4.5.3.1: remove listings of intraocular pressure and dilated fundoscopic examination results
 
29) Section 4.6.1: Update language for Pop-PK analyses
 
CCI [REDACTED]
 
31) Section 6.2.3 updated to align treatment emergent and on treatment definition with collection of AEs per CSP
 
CCI [REDACTED]
 
CCI [REDACTED]
 
34) Section 4.2.3 add PFS rate at 6 months
 
35) Section 4.3.1 add OS rate at 6, 12 and 18 months
 
36) Section 5.2 update sample size determination for 90% power
 
37) Section 4.7 update Table 7 summary of PFS and OS analyses; remove interim analysis for PFS; update OS analyses
 
38) Section 1.2 study design; table for Analysis
 
CCI [REDACTED]
	
SAP amendment 2		TMF-14577505 (20-Apr-2022)	1) PFS primary estimand to be based on investigator-assessed response. PFS based on derived	Change of primary analyses to

SAP Version	Approval Date	Protocol Version (Date) on which SAP is Based	Change	Rationale
			
response removed. Similar changes for ORR, CBR, MRD negativity, DoR, TTR, TTP and CCI
 

2) Section 1.1.2 amend primary estimands and add supplementary estimands for DoR

3) Section 4.2.3 add unstratified cox model

4) 4.2.4.2 add sensitivity analysis on independent review committee (IRC) - assessed response

 
CCI
	
using investigator-assessed response per FDA comments; Amend definition of DoR per FDA comments; Add additional statistical analyses;

## 1. INTRODUCTION

The purpose of this SAP (Version 3) is to describe the planned analyses to be included in the Clinical Study Report for Study 207495.

Additional detail with regards to data handling conventions and the specification of data displays will be provided in the Output and Programming Specification (OPS) document.

### 1.1. Objectives, Estimands and Endpoints

#### 1.1.1. Objectives and Endpoints

Objectives	Endpoints
Primary	

 
To compare the efficacy with belantamabmafodotin vs pomalidomide plus low dose dexamethasone (pom/dex) in participants with relapsed/refractory multiple myeloma (RRMM)
 
	
 
PFS, defined as the time from the date of randomization until the earliest date of documented disease progression (according to IMWG Response Criteria) or death due to any cause
 

Key Secondary	

 
To compare the overall survival with belantamab mafodotin vs Pom/Dex in participants with RRMM
 
	
 
OS, defined as the time from randomization until death due to any cause
 

Secondary	

 
To compare other markers of efficacy of belantamab mafodotin vs pom/dex in participants with RRMM
 
	
 
ORR, defined as the percentage of participants with a confirmed PR or better per IMWG
 
Clinical benefit rate (CBR), defined as the percentage of participants with a confirmed minimal response (MR) or better per IMWG
 
DoR, defined as the time from first documented evidence of PR or better until PD per IMWG or death due to any cause among participants who achieve confirmed PR or better
 
TTR, defined as the time between the date of randomization and the first documented evidence of response (PR or better) among participants who achieve confirmed PR or better.
 
TTP, defined as the time from the date of randomization until the earliest date of documented PD (per IMWG Response Criteria) or death due to PD
 

 
To evaluate the safety and tolerability of belantamab mafodotin vs pom/dex in participants with RRMM
 
	
 
Incidence of adverse events (AEs) and changes in laboratory parameters
 
Ocular findings on ophthalmic exam
 

 
To evaluate the pharmacokinetic profile of belantamab mafodotin
 
	
 
Plasma concentrations of belantamab mafodotin, total mAb, and cys-mcMMAF
 


 
To assess anti-drug antibodies (ADAs) against belantamab mafodotin
 
	
 
Incidence and titers of ADAs against belantamab mafodotin
 

 
To evaluate the tolerability of belantamab mafodotin vs pom/dex based on self-reported symptomatic adverse effects
 
	
 
Symptomatic adverse effects as measured by the PRO-CTCAE and OSDI
 

 
To evaluate and compare changes in symptoms and health-related quality of life (HRQOL) of belantamab mafodotin to pom/dex.
 
	
 
Change from baseline of Health-related QOL as measured by EORTC QLQ-C30, EORTC IL52* and EORTC QLQ-MY20*
 

 
To assess Minimal Residual Disease (MRD) in participants who achieve <math>\geq</math>VGPR or better for belantamab mafodotin vs pom/dex
 
	
 
MRD negativity rate, defined as; the percentage of participants who are MRD negative by NGS method
 

Exploratory	

CCI

CCI

ADA= anti-drug antibodies; AE = adverse event; CCI; CCI; CCI; DOR = duration of response; CCI; EORTC-IL52 = Disease Symptoms domain of EORTC QLQMY20; EORTC QLQC30 = European Organisation for Research and Treatment of Cancer Quality of Life Questionnaire 30 item Core module; EORTC QLQMY20 = European Organisation for Research and Treatment of Cancer Quality of Life Questionnaire 20 item Multiple Myeloma module; CCI; CCI; HRQoL = health related quality of life; IMWG = International Myeloma Working Group; KVA = Keratopathy Visual Acuity; MRD = minimal residual disease; NGS = Next Generation Sequencing; ORR = overall response rate; OS = overall survival; OSDI = Ocular Surface Disease Index; PD = progressive disease; PFS = progression-free survival; CCI; CCI; pom/dex = pomalidomide/dexamethasone; PR = partial response; PROCTCAE = Patient Reported Outcomes version of the Common Terminology Criteria for Adverse Events; QOL = quality of life; RRMM = relapsed/refractory MM; SAE = serious adverse event; CCI; TTP = time to progression; TTR -= time to response; VGPR= very good partial response  
\* = EORTC IL52 applies to participants enrolled under the original protocol; EORTC QLQ-MY20 applies to participant enrolled under protocol amendment 1;

CCI

1.1.2. Estimands

Table 1 Estimands

Objective	Estimand Category	Estimand			Population Level Summary Measure
		Variable/Endpoint	Analysis Set	Intercurrent Event Strategy	
Primary Objective: To demonstrate the superiority of belantamab mafodotin compared to pomalidomide plus low dose dexamethasone (pom/dex) in PFS in participants with relapsed/refractory multiple myeloma (RRMM) [1]	Primary	PFS	ITT	
 
• Disease assessments between scheduled visits: treatment policy
 
• New anti-cancer therapy: while on treatment
 
• Extended loss to follow-up: while on treatment
 
• Treatment discontinuation: treatment policy
 
• Death: composite
 
	Hazard ratio for belantamab mafodotin vs pom/dex
	Supplementary 1	PFS	ITT	
 
• Disease assessments between scheduled visits: hypothetical
 
• New anti-cancer therapy: while on treatment
 
• Extended loss to follow-up: while on treatment
 
• Treatment discontinuation: treatment policy
 
• Death: composite
 
	Hazard ratio for belantamab mafodotin vs pom/dex
	Supplementary 2	PFS	ITT	
 
• Disease assessments between scheduled visits: treatment policy
 
• New anti-cancer therapy: composite
 
• Extended loss to follow-up: treatment policy
 
• Treatment discontinuation: composite
 
• Death: composite
 
	Hazard ratio for belantamab mafodotin vs pom/dex
Key Secondary Objective: To demonstrate the superiority of belantamab mafodotin compared to pomalidomide plus low dose dexamethasone (pom/dex) in OS in participants with relapsed/refractory multiple myeloma (RRMM) [1]	Primary	OS	ITT	Survival benefit regardless of subsequent anticancer therapies or treatment compliance 
 
• New anti-cancer therapy: treatment policy
 
• Treatment discontinuation: treatment policy
 
	Hazard ratio for belantamab mafodotin vs pom/dex

Objective	Estimand Category	Estimand			Population Level Summary Measure
		Variable/Endpoint	Analysis Set	Intercurrent Event Strategy	
Secondary Objectives (Efficacy): To demonstrate the superiority of belantamab mafodotin compared to pomalidomide plus low dose dexamethasone (pom/dex) in ORR/CBR/TTR/TTP/DoR/MRD in participants with relapsed/refractory multiple myeloma (RRMM) [1]	Primary	ORR	ITT	
 
New anti-cancer therapy: while on treatment
 
Treatment discontinuation: treatment policy
 
	>=PR percentage by treatment arm
		CBR	ITT	
 
New anti-cancer therapy: while on treatment
 
Treatment discontinuation: treatment policy
 
	>=MR percentage by treatment arm
		DoR	ITT	
 
Disease assessments between scheduled visits: treatment policy
 
New anti-cancer therapy: while on treatment
 
Extended loss to follow-up: while on treatment
 
Treatment discontinuation: treatment policy
 
Death due to non-PD: composite
 
Death due to PD: composite
 
	Summarized using the Kaplan-Meier method by treatment arm
		TTR	ITT	
 
New anti-cancer therapy: while on treatment
 
Treatment discontinuation: treatment policy
 
	Descriptive summary of TTR by treatment arm
		TTP	ITT	
 
Disease assessments between scheduled visits: treatment policy
 
New anti-cancer therapy: while on treatment
 
Extended loss to follow-up: while on treatment
 
Treatment discontinuation: treatment policy
 
Death due to non-PD: while on treatment
 
Death due to PD: composite
 
	Hazard ratio for belantamab mafodotin vs pom/dex
		MRD	ITT	
 
New anti-cancer therapy: while on treatment
 
Treatment discontinuation: treatment policy
 
	MRD negativity percentage by treatment arm
	Supplementary	DoR	ITT	
 
Disease assessments between scheduled visits: treatment policy
 
New anti-cancer therapy: while on treatment
 
Extended loss to follow-up: while on treatment
 
Treatment discontinuation: treatment policy
 
Death due to non-PD: while on treatment
 
Death due to PD: composite
 
	Summarized using the Kaplan-Meier method by treatment arm

Objective	Estimand Category	Estimand			Population Level Summary Measure
		Variable/Endpoint	Analysis Set	Intercurrent Event Strategy	

- [1]. have received at least 2 prior lines of anti-myeloma treatments, including at least 2 consecutive cycles of both lenalidomide and a proteasome inhibitor (given separately or in combination), and must have documented disease progression as defined by IMWG (a) on, or within 60 days of completion of the last therapy or (b) must be non-responsive while on last treatment, where non-responsive is defined as not achieving at least Minimal Response (MR) after 2 complete treatment cycles. In such cases lack of achieving of MR must be determined no earlier than at least 4 weeks after the last treatment

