### 4.2.2. Planned analysis of PFS

#### Overview of the planned analyses

- Primary analysis of PFS will be based on investigator-assessed response (per IMWG Kumar, 2016)
- Handling of intercurrent events for primary estimand (Table 1) are specified as the primary event and censoring rules in Table 2; Handling of intercurrent events for supplementary estimands 1&2 (Table 1) are specified as the alternative event and censoring rules 1&2 in Table 2, respectively;

The following sets of analyses will be conducted:

- [1]. Primary analysis of primary estimand ( investigator-assessed response + primary censoring rules);
- [2]. Primary analysis of supplementary estimand 1 ( investigator-assessed response + alternative censoring rules 1);
- [3]. Primary analysis of supplementary estimand 2 ( investigator-assessed response + alternative censoring rules 2);

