**Table 2 Assignments for Primary and Alternative Progression and Censoring Dates for PFS Analysis**

Situation	Date of Event (Progression/Death) or Censoring	Outcome Event (Progression/Death) Or Censored
No (or inadequate) baseline tumor assessments  and the subject has not died (if the subject has died follow the rules for death indicated at the bottom of the table)	Randomization	Censored
No post-baseline assessments and the subject has not died (if the subject has died follow the rules for death indicated at the bottom of the table)	Randomization	Censored
Progression documented at scheduled visits and Progression documented without extended loss-to-follow-up time 	Date of assessment of progression	Event
Progression documented between scheduled visits and Progression documented without extended loss-to-follow-up time 	Date of assessment of progression	Event
	Date of next scheduled response assessment [SA1]	Event [SA1]
No progression (or death)	Date of last 'adequate' assessment of response 	Censored
New anticancer treatment started (prior to documented disease progression or death)  .	Date of last 'adequate' assessment of response  (on or prior to starting anti-cancer therapy)	Censored
	Date of starting new anticancer therapy [SA2]	Event [SA2]
Death without extended loss-to-follow-up time 	Date of death	Event
Death or progression after an extended loss-to-follow-up time 	Date of last 'adequate' assessment of response  prior to PD/death (prior to missed assessments)	Censored
	Date of death or progression [SA2]	Event [SA2]
Death or progression after an extended loss-to-follow-up time  from randomization	Date of randomization	Censored
Treatment discontinuation due to clinical PD before PD or death [SA2]	Date of treatment discontinuation [SA2]	Event [SA2]

[SA1]. Alternative rule 1 for handling of intercurrent events for supplementary estimand of PFS

[SA2]. Alternative rule 2 for handling of intercurrent events for supplementary estimand of PFS

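### Supplementary PFS estimand 2: Tables 1 and 2 disagree on which treatment discontinuations are events, and Table 2 leaves one extended-gap case open to two codings

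*SAP*

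**What the plan says.** Table 1 in SAP Section 1.1.2 assigns a strategy to five intercurrent events for each PFS estimand. For Supplementary 2 two of the entries are "Treatment discontinuation: composite" and "Extended loss to follow-up: treatment policy". For the primary estimand and Supplementary 1 the discontinuation entry is "Treatment discontinuation: treatment policy".

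Section 4.2.2 links the estimands to the programming rules: the intercurrent events of supplementary estimands 1 and 2 "are specified as the alternative event and censoring rules 1&2 in Table 2". Lines of Table 2 marked SA2 are alternative rule 2 and so implement Supplementary 2.

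Table 2 then has three relevant rows:

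- **Discontinuation.** The only such row, marked SA2, is "Treatment discontinuation due to clinical PD before PD or death". It is an event dated at discontinuation.
- **Extended gap, general.** Under the primary rule, progression or death after a gap of more than 49 days is censored at the last adequate assessment. The SA2 line makes it an event on the "Date of death or progression".
- **Extended gap, specific.** This row covers progression or death after an extended "loss-to-follow-up time [4] from randomization". It gives censoring at randomization and has no SA2 line.

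**The concern.** Table 2 is meant to carry out what Table 1 defines, so the two should classify the same participant in the same way. For Supplementary 2 they do not on treatment discontinuation, and on extended loss to follow-up the answer depends on which Table 2 row is applied.

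A reader who takes the definition from Table 1 would believe that the reported hazard ratio counts every discontinuation as an event, when the programmed analysis counts only those for clinical progression. In the gap case, two programmers working from Table 2 could code the same participant differently, one as an event and the other as contributing nothing.

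**Working it through.** The check is a comparison of text. The SAP gives no figure for this point that could be reproduced, apart from the gap threshold: 6 weeks × 7 + 7 = 49 days, as stated.

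**Which strategies distinguish Supplementary 2 (Table 1)**

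| Intercurrent event | Primary | Supplementary 2 | Table 2, alternative rule 2 |
|---|---|---|---|
| Assessment between visits | treatment policy | treatment policy | same as primary |
| New anti-cancer therapy | while on treatment | composite | event line present |
| Extended loss to follow-up | while on treatment | treatment policy | event line in one of two applicable rows |
| Treatment discontinuation | treatment policy | composite | event only for clinical PD |
| Death | composite | composite | same as primary, outside the gap rows |

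The two estimands differ on 3 of 5 intercurrent events. Of those 3, Table 2 leaves 2 mismatched or open to two readings.

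**Part 1: discontinuation**

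1. The Table 1 term carries no reason. For the primary estimand and Supplementary 1 the same term covers every reason, because Table 2 has no discontinuation row under those rules.
2. Section 1.2 foresees stopping for reasons other than progression, including unacceptable toxicity, and continues 3-weekly disease evaluation afterwards.
3. Illustrative case: a participant stops for toxicity on day 40, starts no new therapy, is assessed on schedule and has PD on day 120. Table 1 (composite) gives an event on day 40. Table 2 under SA2 has no row for this stop, so the event is on day 120. The participant is in effect handled by treatment policy, not composite.

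**Part 2: extended gap from randomization**

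1. Illustrative case: no adequate post-baseline assessment and death on day 60. Since 60 > 49, the gap is extended.
2. The general row with its SA2 line gives an event on day 60.
3. The from-randomization row gives censoring at day 0. Elsewhere Table 2 prints an SA2 line where alternative rule 2 departs from the primary rule, so a row without one reads as keeping the primary rule.
4. Treatment policy in Table 1 agrees only with the event.
5. Table 2 has no rule of precedence between overlapping rows. Table 3 does (note 4: the first applicable criterion is taken).
6. Under the primary rule both rows censor, so the event-or-censored conflict arises only under alternative rule 2.

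**Size**

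- Part 1: correcting the Table 1 label changes no reported number, only what the number is said to estimate.
- Part 2: a case needs PD or death after day 49 with no adequate result at the first two 3-weekly assessments. If censored at day 0 it contributes neither an event nor follow-up time. Every primary-rule event is also an event under alternative rule 2, so at the ITT target one case is at most 1/151 = 0.0066, or 0.66% of events.

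**The case against.** **Labels and definitions.** Table 1 can be read as naming strategies that Table 2 then defines. Table 2 narrows other labels too: new therapy counts only before progression or death, and only progression found between visits is re-dated. The discontinuation row is itself unambiguous, so no programmer would go wrong. That last point stands, and it is why Part 1 changes no number. The parallel is weaker. The other two restrictions follow from time to first event and from what an assessment can contribute to PFS. Limiting discontinuation to one reason changes which participants have the event.

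**Splitting by cause.** Table 1 does separate causes elsewhere, as in "Death due to non-PD: while on treatment" for TTP and supplementary DoR. However, primary DoR also splits death by cause although both parts are composite. The split shows that the table can express a cause; it does not prove what was intended here.

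**The gap rows can be reconciled.** The from-randomization row may exist only to supply a primary-rule censoring date when there is no adequate assessment, with the general row's SA2 event covering the case. This reading is possible and agrees with Table 1. Table 2 does not state it, though, and the literal reading of the specific row contradicts Table 1.

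**Section 6.2.9** repeats the censoring without an SA2 exception, but does so for the general row as well, which plainly has one. It therefore describes the primary rule and is not evidence for either reading.

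**The 0.66%** is a share per case, not an effect size. It rests on an approximate target of 151 in ITT and does not carry over to mITT, which may have fewer events. This is accepted.

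**Conclusion.** The concern holds, as a minor one. On treatment discontinuation, alternative rule 2 does not implement Supplementary 2 as Table 1 labels it. On the extended gap from randomization, the specific row read literally gives a result that contradicts both Table 1 and the general row's SA2 line, and nothing in Table 2 says which row governs.

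The scope is the Supplementary 2 Kaplan-Meier and Cox estimates in ITT (Section 4.2.5.1) and mITT (Section 4.2.5.2). Section 4.2.3 reserves the stratified log-rank test for the primary estimand, so no test is attached to them. Primary PFS, its event trigger, alpha and power are unaffected.

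The total effect cannot be derived, because the SAP gives no rates of discontinuation by reason or of missed early assessments. Which discontinuations the sponsor meant to count is also not established by the text.

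**What to change.** Reconcile the tables before the data are seen.

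1. **Discontinuation.** If Table 2 states the intention, change the Supplementary 2 entry in Table 1 to composite for discontinuation due to clinical PD and treatment policy for other reasons. The continued disease evaluation in Section 1.2 supplies the data. If all discontinuations were meant, widen the SA2 row of Table 2 instead. The first is the simpler change because Table 2 is the operative and more specific text.
2. **Gap from randomization.** Add an SA2 line to that row of Table 2, making the case an event on the date of death or progression. Table 1 and the general row's SA2 line already agree on this.
3. **Section 6.2.9.** Add one sentence saying that its censoring does not apply under alternative rule 2.

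The cost is wording in two tables and one sentence. No new data are needed.
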